1 PROTOCOL SUMMARY

- Title:** Pilot Study of Robotic-Assisted Harvest of the Latissimus Dorsi Muscles.
- Design:** Single-Center, Non-Randomized, Prospective Study of the *da Vinci® surgical system* in Latissimus Dorsi Muscle Flap Harvest Procedures.
- Purpose:** To evaluate the safety and feasibility of the *da Vinci® surgical system* in minimally invasive muscle flap harvest procedures.
- Enrollment and Sites:** A maximum of 15 subjects requiring a muscle flap harvest for subsequent breast, scalp, upper extremity, or lower extremity reconstructive surgery will be enrolled at The University of Texas MD Anderson Cancer Center (MD Anderson) in Houston, Texas.
- Study Duration:** Initial Enrollment: Q1'15
Last Enrollment: Q2'17
Last Follow up: Q4'17
- Subject Follow up:** 0-2 weeks, 2-4 weeks, 1-3 months, and 3-6 months post-procedure.
- Study Endpoints:** Primary Safety Endpoint:
The primary safety endpoint is muscle flap failure.
- Secondary Endpoints:
1. Evaluation of donor site complications through 6 months post-procedure.
 2. If the flap is for external use, interval viability with a Doppler proximally and distally will be checked at 3 months post-procedure.
 3. If the flap is for pedicled, internal use over an implant, no additional evaluation will be possible unless planned or unplanned reoperation exposes the muscle, at which

time a Doppler evaluation would be undertaken.

4. Conversion rate (i.e., completion of the latissimus dorsi harvest procedure with the *da Vinci® Robotic Surgical system* without converting to an open procedure).
5. The validated QuickDASH questionnaire to evaluate postoperative shoulder function as compared to preoperative QuickDASH shoulder function.
6. Postoperative pain assessed by validated visual analog scale (VAS).
7. Physical therapy assessment of range of motion and strength of the affected shoulder using the validated American Shoulder and Elbow Surgeons (ASES) assessment tool.
8. Length of stay and analgesic use to be compared to historical controls of the open procedure.

**Study Inclusion
Criteria:**

1. The subject must be equal to or greater than 18 years of age.
2. The subject must be willing and able to provide informed consent.
3. The subject is willing and able to comply with the study protocol.
4. The subject is undergoing one of the following reconstructive procedures that requires latissimus dorsi muscle harvest:
 - a. Post-mastectomy breast reconstruction procedure (either nipple or skin sparing) in which a female subject needs additional muscle coverage over an implant, but does not need additional skin (i.e., patient is a candidate for a pedicled latissimus dorsi muscle flap procedure); OR,
 - b. Scalp reconstruction procedure in which the subject needs a free latissimus dorsi muscle flap for wound coverage; OR,
 - c. Upper extremity reconstruction procedure in which the subject needs a free latissimus dorsi muscle flap for wound coverage; OR,
 - d. Lower extremity reconstruction procedure in which the subject needs a free latissimus dorsi

muscle flap for wound coverage.

5. The subject agrees to follow up examinations out to 6 months post-procedure.

Study Exclusion Criteria:

1. The subject has a BMI > 35.
2. The subject has a history of significant bleeding disorders.
3. The subject is diabetic.
4. The subject is known or suspected to be pregnant or lactating.
5. The subject has a history of peripheral vascular disease.
6. The subject is a current smoker (has smoked within 4 weeks prior to surgery).
7. The subject has had prior back or axillary surgeries which could compromise the blood supply of the flap.

Study Monitor:

The University of Texas MD Anderson Cancer Center,
Monitoring Services – IND Office
[name]

Principal Investigator:

[name]
Board Certified, Plastic and Reconstructive Surgery
The University of Texas MD Anderson Cancer Center
Julie Kyte Center for Reconstructive Surgery
[name]

Data Analysis:

The University of Texas MD Anderson Cancer Center
Department of Plastic Surgery, Unit 1488
[name], Principal Statistical Analyst,
[name], Metrics Analyst
[name]

2 INTRODUCTION

The purpose of this clinical study is to evaluate the safety and feasibility of the *da Vinci*® surgical system used in minimally invasive muscle harvest of either a free or pedicled

latissimus dorsi muscle. In this study, the harvested muscle will be used in breast, scalp, upper extremity or lower extremity reconstruction procedures as these are anticipated to be the highest volume use for these muscle flaps. However, the procedure under study is for robotic-assisted muscle harvest only, not the subsequent manually performed surgical reconstruction. Any type of reconstruction for which a free or pedicled latissimus dorsi flap is deemed to be medically necessary would benefit from this potentially less invasive harvest. As such, the endpoints of the study are aimed at evaluating safety, donor site morbidity, and the integrity and viability of the harvested muscle prior to the reconstruction procedure. The *da Vinci*® robotic surgical system is intended to assist in the accurate control of surgical endoscopic instruments. The system is currently FDA cleared for a variety of urologic, gynecologic, cardiothoracic and transoral otolaryngologic procedures. However, the device has not been specifically evaluated for latissimus dorsi muscle flap harvest. As such, the purpose of this study is to evaluate the safety and feasibility of the *da Vinci*® robotic surgical system for use in this specific procedure.

This is a prospective, non-randomized, single-arm study that will be conducted at The University of Texas MD Anderson Cancer Center (MD Anderson) in Houston, Texas. Up to 15 subjects requiring latissimus dorsi muscle harvest in conjunction with breast, scalp, upper extremity or lower extremity reconstructive procedures will be enrolled. The primary safety objective of this study is to evaluate the muscle flap failure. The efficacy endpoint is to assess flap viability at harvest via doppler and clinical examination. Secondary efficacy endpoints include postoperative assessment through quantitative (QuickDASH questionnaire), pain assessment (VAS), and a Physical Therapy assessment of the patient's range of motion and strength of the shoulder from which the latissimus dorsi muscle was harvested. All enrolled subjects will have four follow up visits (at 0-2 weeks, 2-4 weeks, between 1-3 months, and between 3-6 months post-procedure). The following section provides background information regarding current surgical methods for muscle flap harvest procedures.

3 BACKGROUND

3.1 Worldwide Clinical Usage of the *da Vinci*® Robotic Surgical system

The *da Vinci*® surgical system (s) is a robotic platform for minimally invasive surgery initially cleared by the U.S. Food and Drug Administration (FDA) for use in general laparoscopic surgery in 2000. Since then, it has received numerous clearances for a variety of indications for use, including general surgery, urologic, gynaecologic, thoracic, cardiac, and pediatric surgery. The *da Vinci*® robotic surgical system(s) has provided surgeons with the clinical and technical capabilities of traditional open surgery while enabling them to operate through small incisions. Each tiny incision (approximately 1cm), or port, involves insertion of an instrument which may be independently controlled by a

robotic arm on the *da Vinci*® robotic surgical system's patient-side cart. Robotic-assisted surgery may provide benefits to the patient including, but not limited to, shorter hospital stays, reduced rates of complications and a quicker return to normal activities as compared to open surgery.

From 2000 to present, over 800,000 robotic procedures facilitated by *da Vinci*® surgical system have been performed across a broad spectrum of surgical specialties around the world. Over 40 510(k) s have been FDA cleared for various device modifications and new indications for use. This commercial experience demonstrates the wide applicability of the system for use in common surgical tasks such as grasping, cutting, dissection, coagulation, etc. No new types of surgical tasks, or new instrument types will be required for use of the system in latissimus dorsi flap harvest procedures.

3.2 Literature Review - Latissimus Dorsi Muscle Harvest Procedures

Plastic surgeons frequently transport vascularized muscle from one part of the body to another, either as a free flap, in the case of lower extremity or scalp coverage, or as a pedicled flap, in the case of breast reconstruction and chest wall reconstruction. One of the most common muscle flaps employed to this end is the latissimus dorsi muscle flap. One problem with the harvest of this large muscle during an open surgical procedure is that the donor incision required to remove it from the orthotopic position is generally around 25 cm – 30 cm. For reconstructing, when overlying skin is a necessary part of the intended reconstruction, the harvest incision doubles as the skin harvest site. However, where only the muscle is required, the large skin incision is only for access and affords no benefit to the patient. Such procedures leave an unnecessary, long, conspicuous scar on the patient's back or flank.

In an effort to reduce unnecessary donor site incisions and related morbidity, endoscopic techniques for latissimus dorsi muscle harvest have been developed to reduce the amount of scarring associated with open procedures. Several authors have reported on these endoscopic techniques for free and pedicled flap harvesting^{1,5}. The endoscopic approach has been abandoned in many centers as a result of technical challenges posed by cumbersome instrumentation, and more sophisticated instrumentation has been deemed necessary to facilitate the endoscopic approach in the subcutaneous space⁷.

The following two sections discuss the current literature on endoscopic harvest of latissimus dorsi flaps and the utility of pedicled and free latissimus dorsi (muscle only) flaps, respectively.

Endoscopic Pedicled Latissimus Dorsi Flap for Breast Reconstruction

In 2007, Missana, et al reported on the results from a study of 52 patients who underwent latissimus dorsi endoscopic harvest for immediate breast reconstruction after a skin-sparing mastectomy¹. The authors developed this technique to decrease the morbidity of the donor site. The technique involves preparation of the site with lighted forceps, followed by endoscopic dissection after a neocavity is formed by insufflating CO₂. The mean surgical endoscopic time was 64 minutes and there was one procedure that converted to an open procedure. Complications included: 2 hematomas, 6 inflammatory syndromes and 1 pulmonary embolism. While 4 patients had skin flap necrosis during the reconstruction portion of the case, none of the patients had donor site necrosis complications during the latissimus dorsi flap harvest. The average length of hospital stay was 5.6 days. The dorsal drain was removed 15 days post-procedure. The authors concluded that endoscopic harvesting of the latissimus dorsi flap performed using the prescribed technique is feasible, reproducible and permits a significant reduction of incision size (2 cm as compared 20 cm with open surgery) and postoperative pain with good aesthetic results. The authors noted that this procedure was not recommended for patients who are overweight or in patients who smoke because of the significant rate of necrosis in the anterior thoracic cutaneous flaps.

In 2000, Ramakrishnan et al reported on 12 patients requesting breast reconstruction of a “high-risk” chest wall⁴. Endoscopic latissimus dorsi muscle harvest was conducted to cover an expander placed within an endoscopically created chest wall pocket. Of the 11 patients who underwent an oncological procedure, 8 of these patients received radiation therapy and 5 received chemotherapy. Additionally, 5 of these patients were smokers who smoked more than 10 cigarettes per day. Five of the 12 operations were performed through single-port access and the remaining 7 were performed with the addition of a bra strap port. Based on this case series, the authors advocated the use of two ports for operational ease and efficiency. The best muscle harvest time achieved was 60 minutes. Five of the 12 patients received blood transfusions; in all of these patients, the procedure had been initially attempted through a single port. While the authors noted acceptable results with their endoscopic technique, they concluded that improved instrumentation concerning the creation and maintenance of optical space would need to be developed before this technique was widely adopted.

In 2004, Losken, et al reported on their experience with endoscopic-assisted harvest of latissimus dorsi muscles for reconstructing partial mastectomy defects². The authors sought to evaluate the risks and benefits associated with immediate versus delayed muscle flap transfers. Thirty-nine cancer patients with an average follow up of 3.67 years were included in this review. Donor site complications occurred in 12 patients and included: seromas (7), hypertrophic scarring (1), skin loss (1) and wound dehiscence (1). One patient experienced postoperative lymphedema and another had a persistent sinus

tract requiring excision with pectoralis muscle flap reconstruction. To reduce the risk of cancer recurrence following mastectomy procedures, the authors recommended confirmation of negative margins prior to latissimus dorsi muscle transfer.

In 1998, Masuoka, et al reported on 7 patients who underwent breast reconstruction surgery with the latissimus dorsi muscle flap combined with a saline implant using an endoscopic approach for muscle harvest⁶. The authors employed the use of a modified endoscopic technique performed through a larger incision due to former surgery. This approach proved easier than standard endoscopy because the procedures were performed under direct visualization. As such, this methodology maximized acquisition of optical space, a limitation of subcutaneous endoscopic surgery. The authors concluded that harvesting a latissimus dorsi muscle flap using an endoscope was a useful method to avoid additional scarring.

Free Latissimus Dorsi Flap Literature

In a 1990 review conducted by Furnas, 18 patients underwent scalp reconstructions of complicated scalp wounds with 21 free flaps: 11 from the latissimus dorsi, 3 scalp transfers between identical twins, 3 groin, 1 combined latissimus dorsi and serratus anterior, 2 serratus anterior, and 1 omentum³. All of the flaps survived with follow up ranging from 3 weeks to 7 years. The latissimus dorsi was shown to be their first choice for free flap reconstruction of scalp wounds because of its large size, predictable blood supply, ease of harvesting, and provision of excellent vascularity to compromised beds.

Many other additional studies since then have confirmed the popular use of the latissimus dorsi free flap for scalp reconstruction. The complication rate is low and cosmesis was satisfactory¹⁰.

In 1997, Cho, et al reported on 10 patients with lower extremity reconstructive procedures which utilized free latissimus dorsi muscle flaps⁷. Muscle harvest was accomplished endoscopically with a 5-6 cm incision. The largest harvested muscle was 15 x 25 cm. An average time of 2-3 hours was required for muscle flap harvest. No donor site complications such as hematomas or seromas were observed. The patients were satisfied with the short donor site scars and reported decreased postoperative pain. The authors concluded that endoscopic harvesting techniques had several limitations. Specifically, they opined that the key to successful endoscopic free flap transfer is operative dexterity, experience and access to proper instrumentation. They also emphasized the need for good visualization and proper hemostasis to avoid complications.

3.3 Conclusion

Endoscopic approaches for either a pedicled or free latissimus dorsi muscle flap harvest have been successfully employed. However, there are a variety of problems with the endoscopic approach⁷. One problem is that the optical window is very tight, preventing visualization of the appropriate anatomic structures that allow for safe harvest.

Instrumentation presents a second issue; endoscopic instruments are long and unwieldy, making precise dissection and hemostatic management challenging, particularly in the context of difficult retraction and poor visualization. These impediments have impaired widespread adoption of minimally invasive techniques for muscle harvest procedures.

In this study, we hypothesize that the *da Vinci*® robotic surgical system may offer distinct advantages for enabling surgical harvest of the latissimus dorsi flap through small incisions. The advantages of the robotic platform are precision and visualization which are anticipated to address many of the reported issues such as bleeding and flap necrosis by allowing the surgeon to better monitor and control their surgical technique. By creating an optical window with the use of insufflation, camera and instruments can be comfortably positioned within tight spaces to operate using very precise movements. Because incisions are limited to three ports, the largest of which is 1.2 cm, this technology is well suited to minimally invasive muscle harvest, and solves some of the challenges that endoscopic flap harvest presents.

In summary, a variety of endoscopic surgical techniques have been proposed over the past 15 years to harvest latissimus dorsi muscle flaps but none have achieved widespread adoption despite a strong patient benefit. It is hoped that robotic-assisted latissimus dorsi flap procedures will help overcome some of the limitations inherent in the current endoscopic approaches. This study seeks to evaluate the safety and feasibility of this robotic-assisted approach and will evaluate donor site complications and flap survival in patients requiring latissimus dorsi muscle harvest for subsequent breast, scalp, upper extremity, and lower extremity reconstructive procedures.

4 PRIOR INVESTIGATIONS

Robotic-assisted latissimus dorsi muscle flap harvests have been completed using the *da Vinci*® robotic surgical system in 10 cadavers and 15 clinical patients. All procedures were completed by the Principal Investigator for this proposed study. A summary of the procedures completed by [name], is provided below.

4.1 Cadaver Evaluation

Ten robotic latissimus dorsi muscle harvests were performed in 10 cadavers from 2009 to 2010⁸. All dissections were performed by the study's principal investigator, [name],

MD, using the *da Vinci*® robotic surgical system. All 10 latissimus dorsi muscles were harvested successfully in their entirety. The goal of these cadaveric studies was to develop and refine the port placement, workflow and operative technique. [name] concluded that the robotic-assisted endoscopic harvest technique was both feasible and reproducible.

5 INTENDED USE

The *da Vinci*® robotic surgical system is intended to assist in the accurate control of Intuitive Surgical endoscopic instruments during latissimus dorsi muscle flap harvest procedures in patients scheduled to undergo subsequent reconstruction procedures which require a muscle only flap (free or pedicled). In this study the free flaps will be used for scalp, upper extremity, and lower extremity reconstruction and pedicled flaps will be used for breast reconstruction. The *da Vinci*® robotic surgical system is intended for use by trained physicians in an operating room environment in accordance with the system User Manual (Appendix I) and this clinical protocol.

6 STUDY DEVICE

6.1 Description

The *da Vinci*® robotic surgical system is a computer assisted device designed to facilitate complex surgery using a minimally invasive approach. The system consists of the following 3 main components: 1) Surgeon Console; 2) Patient Cart; and, 3) Vision System Cart. These components are described below and depicted in Figure 1.

Surgeon Console: is the control center for the system. While seated at the surgeon console (outside of the sterile field) and as observed through the console's stereo viewer, the surgeon controls critical aspects of the surgical procedures, including movement of the endoscopic instruments and endoscope within the operative field. Instrument and camera movements are controlled by the surgeon through the use of 2 hand operated controllers residing in the console and foot pedals at the console's base. These features allow the surgeon to be as dexterous as in "open" surgery, while operating in a minimally invasive environment. The surgeon at the console also has the option to change the surgical view from full screen mode to a multi-image mode, which displays the 3-dimensional (3-D) image of the operative field.

Patient-Side Cart: is the operative component of the surgical system within the sterile field. Its primary function is to support the EndoWrist® instrument arms and camera arm during surgical procedures. EndoWrist instruments are designed to provide surgeons with natural dexterity and a greater range of motion than the human hand. This allows for greater precision when operating in a minimally invasive environment. EndoWrist instruments are designed to support rapid and precise suturing, dissection and tissue manipulation in surgical procedures.

Vision System Cart: houses the system's imaging processing equipment and is operated by a person outside of the sterile field during surgery. The cart provides space for an

optional touch screen monitor as well as ancillary surgical equipment. The cart consists of a stereo endoscope, endoscopic camera and various accessories including a light source and light guides. The Insite Vision System provides 2 independent images that are relayed to the viewer located in the surgeon console, where they are used to form a 3D image (or alternatively 2D) of the surgical field for the surgeon's reference.

Figure 1: Overview of the *da Vinci*[®] System (Console, Patient-side Cart and Vision System)

6.2 Device Requirements

The *da Vinci*[®] robotic surgical system is available commercially for a variety of cleared indications. MD Anderson currently has the *da Vinci*[®] Si system at their facility in use for transoral robotic surgery (TORS), prostatectomy, hysterectomy, thoracic procedures, and general surgeries. The existing *da Vinci*[®] Si system will be used in conjunction with standard commercially available *da Vinci*[®] instruments including: monopolar curved scissors, Maryland with bipolar, Cadiee grasping forceps, and 3D endoscopes.

7 STUDY OBJECTIVES

The objective of this study is to evaluate the safety and feasibility of the *da Vinci*[®] robotic surgical system in 15 subjects undergoing latissimus dorsi muscle flap harvest procedures in conjunction with breast, scalp, upper extremity, and lower extremity reconstruction procedures. Donor site complications and flap viability will be assessed intraoperatively and through 6 months post-procedure, and length of stay and analgesic use as an inpatient will be compared to historical controls of the open approach.

8 STUDY ENDPOINTS

8.1 Primary Safety Endpoint:

The primary safety endpoint is muscle flap failure.

8.2 Primary Efficacy Endpoint:

Latissimus dorsi muscle flap viability evaluated by clinical assessment and doppler examination at the end of the muscle harvest portion of the surgical procedure.

8.3 Secondary Endpoints:

1. Evaluation of donor site complications through 6 months post-procedure.
2. If the flap is for external use, interval viability with a Doppler proximally and distally will be checked at 3 months post-procedure.
3. If the flap is for pedicled, internal use over an implant, no additional evaluation will be possible unless planned or unplanned reoperation exposes the muscle, at which time a Doppler evaluation would be undertaken.
4. Conversion rate (i.e., completion of the latissimus dorsi harvest procedure with the *da Vinci*® *Robotic Surgical system* without converting to an open procedure).
5. The validated QuickDASH questionnaire to evaluate postoperative shoulder function as compared to preoperative QuickDASH shoulder function.
6. Postoperative pain assessed by validated visual analog scale (VAS).
7. Physical therapy assessment of range of motion and strength of the affected shoulder using the validated American Shoulder and Elbow Surgeons (ASES) assessment tool.
8. Length of stay and analgesic use to be compared to historical controls of the open procedure.

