9 METHODS

9.1 Study Design

This is a prospective, non-randomized, single-arm study of the *da Vinci*® robotic surgical system in subjects undergoing latissimus dorsi muscle flap harvest procedures in conjunction with breast, scalp, upper extremity and lower extremity reconstructive procedures. This study will be conducted at MD Anderson in Houston, Texas. Muscle flap failure and donor site complications will be assessed through 6 months post-procedure. Flap viability will be assessed following completion of the robotic-assisted harvest procedure. Flap viability is defined as having a pink, non-congested appearance and an audible arterial and venous Doppler signal. Additional assessments of viability will include bleeding at the distal extremes of the muscle when cut sharply, and an audible Doppler signal detected in the distal third of the muscle.

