9.4.2 Exclusion Criteria

Subjects will be excluded from this trial if any of the following criteria are met:

- 1) The subject has a BMI > 35.
- 2) The subject has a history of significant bleeding disorders.
- 3) The subject is diabetic.

- 4) The subject is known or suspected to be pregnant or lactating.
- 5) The subject has a history of peripheral vascular disease.
- 6) The subject is a current smoker (has smoked within 4 weeks prior to surgery).
- 7) The subject has had prior back or axillary surgeries which could compromise the blood supply of the flap.

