12.1 Study Power and Sample Size

The specific sample size for this investigation is not based on the testing of a specific hypothesis with a degree of power to detect a difference. As such, a maximum of 15 subjects will be enrolled in the study with the intent of establishing baseline outcomes for this procedure.

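### Length of stay and inpatient analgesic use are to be compared with historical controls defined only as open, with no eligibility, flap-type or case-mix restriction and no adjustment

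*Combined protocol and SAP*

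**What the plan says.** The comparison appears in the protocol summary, in section 8.3 item 8 ("Length of stay and analgesic use to be compared to historical controls of the open procedure") and in the study objective itself, where section 7 says that "length of stay and analgesic use as an inpatient will be compared to historical controls of the open approach". Section 9.1 describes the design: "This is a prospective, non-randomized, single-arm study". There is therefore no concurrent comparator.

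No section gives the source, centre, calendar period, number, eligibility, flap type or recipient site of the historical controls. Section 12 lists length of stay and pain medication among the outcome variables but attaches no comparative method to them, and section 12.3 names only the software. BMI, smoking and radiation history, defect characteristics and type of reconstruction will be recorded for trial subjects, but nothing says they will be used for adjustment.

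The robotic arm, by contrast, is tightly defined. Section 9.4.2 excludes BMI above 35, significant bleeding disorders, diabetes ("The subject is diabetic"), pregnancy or lactation, peripheral vascular disease, smoking in the four weeks before surgery, and earlier back or axillary operations that might impair the flap's blood supply. Section 5 limits use to muscle-only flaps: pedicled for breast, free for scalp and limbs. Section 3.2 notes that open harvest also serves patients who need skin: "when overlying skin is a necessary part of the intended reconstruction, the harvest incision doubles as the skin harvest site".

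On sample size, section 12.1 says "The specific sample size for this investigation is not based on the testing of a specific hypothesis with a degree of power".

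**The concern.** A selected group of robotic patients may be set against open cases that were not selected in the same way. Patients with diabetes, vascular disease, a high BMI or recent smoking can plausibly be expected to stay longer and have more complications. If they are among the controls and barred from the robotic arm, part of any difference is selection.

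Flap type matters for a second reason. Section 2 limits the study to the harvest, but length of stay and inpatient analgesics follow the whole operation, including the manual reconstruction. A different balance of free and pedicled flaps therefore feeds straight into both outcomes.

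Shorter stay is among the possible robotic advantages raised in section 3.1, while section 10.2 acknowledges that no benefit is proven for this procedure. This comparison is the only place where the trial sets robotic against open patients. With the control pool left undefined, it could also be chosen after the robotic results are known.

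**Working it through.** The plan gives no effect size, SD, control number or test for this comparison, so there is no stated figure to reproduce. The calculations below show how large the bias could be. Inputs not taken from the protocol are marked as assumptions.

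**1. Flap mix.** With no device effect, the apparent saving in stay for the robot is

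(free share in controls − free share in trial) × (extra days for a free flap).

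- Free share in trial: 20%, from the earlier robotic series in section 4.2 (3 free, 12 pedicled; 3/15). The present trial has no quota, so using this share is an assumption. The same section later speaks of the free flaps as if there were two.
- Extra days for a free flap: 1 to 3 (assumption).
- Free share in controls: 10% to 80% (assumption).

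| Free share in controls | 1 day longer | 3 days longer |
|---|---|---|
| 10% | −0.1 × 1 = −0.1 | −0.1 × 3 = −0.3 |
| 20% | 0 | 0 |
| 50% | 0.3 × 1 = 0.3 | 0.3 × 3 = 0.9 |
| 80% | 0.6 × 1 = 0.6 | 0.6 × 3 = 1.8 |

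Positive values favour the robot. If instead the trial were 50% free and the controls 20%, the robot would look 0.3 to 0.9 days worse. The sign depends on a mix that the plan does not fix on either side.

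**2. Selection.** Apparent saving = share of controls with an excluded trait × extra days for that trait. With 10% to 40% of controls affected and 0.5 to 2 extra days (assumptions), this runs from 0.1 × 0.5 = 0.05 to 0.4 × 2 = 0.8 days. Provided the excluded traits lengthen stay, this term can only favour the robot.

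**3. What a bias of that size would do.** Suppose someone applied a two-sided 5% test, which the plan does not specify. The chance of a nominally significant false benefit is about Φ(bias/SE − 1.96), with SE = SD × √(1/15 + 1/n controls). Take a bias of 0.8 days and an SD of 2 days (assumptions):

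- 15 controls: SE = 0.73, chance 19%
- 30 controls: 24%
- 60 controls: 28%
- 100 controls: SE = 0.55, chance 30%

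Without bias the figure is 2.5%. A larger pool of unsuitable controls makes the problem worse, because the interval narrows around a biased value.

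**4. Dependence of the two outcomes.** Section 7 specifies inpatient use but no metric or window. If use is totalled, total = daily use × days. Section 3.2 quotes a 5.6-day mean stay from an endoscopic breast series. That series is neither robotic nor open, so it serves only for scale. A stay one day shorter at the same daily use cuts the total by 1/5.6 = 17.9%.

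**The case against.** The strongest reply is that the plan is silent, not wrong. It never says that the controls will be a broad open population. Since section 5 restricts the study to muscle-only flaps and section 3.2 separately describes open access where only muscle is needed, the open procedure could mean the open version of the same operation. This is also the last of eight secondary endpoints in a pilot of at most 15 subjects. Section 12.1 disclaims hypothesis testing and describes the intent as baseline outcomes: "a maximum of 15 subjects will be enrolled in the study with the intent of establishing baseline outcomes for this procedure". No test or success criterion is attached, so a descriptive reading is already close to the text.

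Much of this stands. The controls are undefined, and a reader who infers that the sponsor has chosen an unrestricted pool goes beyond the text. A reader might also infer that every source of bias favours the robot, but the flap-mix table shows both signs. Nor are the two outcomes one comparison counted twice: analgesic use also depends on daily requirement, and the plan does not say that it will be totalled. The trial does contain other comparisons (QuickDASH and shoulder assessment against baseline, flap failure against a fixed 10%), but none involves another group of patients.

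What the reply does not remove is that a robotic-versus-open comparison is promised in the objective, and nothing in section 12 would prevent a crude one.

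**Conclusion.** The concern holds as a gap in control selection and analysis. The controls are described only as open, the robotic arm is selected and muscle-only, and no adjustment is planned. A crude comparison tends to favour the robot through the exclusions. Differences in flap mix can add to that or offset it, from 0.3 days against the robot to 1.8 days in its favour with 20% free flaps in the trial. If analgesics are totalled over the stay, the two outcomes are strongly dependent.

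The day figures rest on assumed stay differences and control mixes. Only the 3-in-15 share comes from the protocol, and it describes an earlier series. They show plausible size and do not predict a result. The primary safety and efficacy endpoints and the stopping rule are unaffected, so this is a worthwhile, inexpensive improvement and not a threat to the trial's main conclusions.

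**What to change.** Amend section 8.3 item 8 and section 12 to state:

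- **Controls:** open, muscle-only latissimus harvests, preferably at the same centre, in a fixed recent period named before robotic results are examined, in patients who would have met inclusion criterion 4 and exclusion criteria 1 to 7.
- **Flap mix:** standardise or weight the controls to the trial's free/pedicled mix. Alternatively, compare within the pedicled breast stratum and only list the free-flap cases if they are few. At 20% there would be about 3 of 15, too few for a useful stratum.
- **Analgesic use:** express it per inpatient day or over a fixed early window.
- **Reporting:** give differences with 95% CIs, labelled descriptive, with no claim of superiority.

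With this, the flap-mix term goes to zero and the selection term does so for the listed criteria. Differences in care over calendar time remain.

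The cost is plan text, some record review to apply the criteria, fewer controls and a wider interval. At an assumed SD of 2 days, the 95% half-width for 15 robotic subjects is 1.96 × 2 × √(1/15 + 1/60) = 1.13 days with 60 controls and 1.24 with 30. For a breast stratum of 12 against 30 controls it is 1.96 × 2 × √(1/12 + 1/30) = 1.34 days. If published series are the only available controls, the criteria cannot be applied patient by patient, and the report should say so.
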